#### **B. Knowledge of HIV and attitudes towards testing for HIV?**

1. You have decided to accept/ decline offer of HIVST, what other method (s) for testing for HIV do you know?
2. What are the advantages and disadvantages of testing for HIV using this/ these method (s)?
3. How often do you test for HIV and why? It usually takes a long time/ a short time before you test, why? (probing for attitudes)
4. How often do you come to access HIV services here and why?

#### **C. Knowledge about HIVST**

1. What do you know about HIVST?
2. How does it work or not work for you- in your situation? (probe for advantages and disadvantages)

#### **D. Receiving kit from partner**

I would like to learn more about your experience of receiving the HIVST kit from your partner

1. How did your partner tell you about the test kit? What is your view about how the test kit was given to you?
2. When offered the kit? What made you accept/refuse to test? How did the way this was done influence your decision?
3. How did receiving a kit from your partner make you feel? What thoughts came to your mind as you received the kit (probe about trust, about knowledge of own HIV status)
4. What was your immediate response to your partner's request of you testing? Probe: did you test or not? Did you test on your own or you tested as a couple?
5. Are there any beliefs that influenced your decision? What beliefs/ issues influenced your decision? (masculinity, religion, rumours about HIVST Kits)
6. Can you please describe to me what has happened after the kit was given to you? (probe if participant has tested, ask him/her to describe to you how they tested themselves, how easy or difficult was it to do the test, were the instructions easy to follow, any other challenges, what about reading and interpreting the results)

**E. For those testing negative: ask the following questions:**

1. After testing and reading of results, what did the client do?
2. Did you trust the results, or did you doubt them?
3. Did the client think of linking to MMC services (for male participants)?
4. How did the client dispose of the used test kit?
5. (For those who are negative) How easy or difficult was it to access prevention services- condoms, VMMC, PMTCT (for those who tested negative and are willing to share experience)

**F. Linkage to care (only those who have used the test kit. Find out from the onset if participant is willing to talk about their HIV status)**

1. After testing and reading of results, what did the client do?
2. Did you go to the facility for a confirmatory test? Tell us about your experience (what influenced your decision, where was the test conducted if it was done). Probe: why did you decide to conduct a confirmatory test? trust of test kit, partner support,
3. How easy or difficult was it to have a confirmatory test done? Probe: availability of testing services, location of testing services, stigma, attitude of HCWs,
4. In your opinion, are there barriers of linkage to confirmatory testing?
5. Did you get any form of counselling on linkage to care whilst getting a confirmatory test? After the confirmatory? What followed? Where you advised to start treatment? What decision did you make? Did you start treatment? If so, how long did it take for you to

decide and get linked to the clinic for treatment? Did you make this decision after self-testing or was it made after getting a confirmatory test?

- a. What other factors (things) facilitated your decision to start treatment? Probe:
- b. (For those who have not started treatment) What made you not to start treatment? Probe: distance to the clinic, congestion, fear of being seen? feeling healthy,
6. Do you think counselling is important for someone self-testing? If so why? Where you counselled about linking into care? Did this counselling help you decide to link into care?
7. **For clients that decided to link on their own after self-testing:** What was your experience with making the decision for getting linked without anyone counselling you? Do you think counselling is important?
8. In your opinion, what are the other barriers for linkage to care?
9. What can be done to help people who receive kits through their partner link to care?

#### **G. Power, social relations and social harms**

1. You accepted/ rejected offer of HIVST. How did your relationship with your partner influence your decision?
2. How has bringing of the test kit by your partner affected your relationship (probe on support, trust, anger, violence)
3. What role did your partner play as you tested using the test kit? How influential was your partner in the process? (Probe if the participant experienced forced testing, forced disclosure, was supervised during testing when they did not want to)
4. How is your relationship with your partner after they brought home the test kit for you? Probes: did you have any problems because of the test kits? What kind of problems did you have?
5. How can such incidents (Problems) be detected and recorded by us that are giving out the test kits?
6. How can such incidents be prevented in a home?
7. Where can one report such incidents?

We have come to the end of the interview. Thank you

### **Qualitative-Cohort: In-depth Interview for Index partner (second interview)**

**Recap of the last interview:** Thank you for taking time to speak with me today. Last time we talked about to you about your experiences of receiving the test kit from your partner. Our discussion today is just a follow up to see how you are doing and what has changed after our first interview:

#### **A. Social harms**

##### **For clients that experienced social harms**

1. After you offered the test kit to your partner, you mentioned to us that this brought about some problem in your home. Apart from what you told us last time, did you experience any additional problems with your partner? (Probe: on the last harms that were reported) Has your relationship with your partner now changed in any way after our last discussion?
2. Looking back on what happened, how did you sort out these problems? (Probes: who did you consult? clinic staff, CHW, family members etc.)
3. Looking back on what happened, is there anything you can do differently if you were to deliver a test kit to your partner again?
4. What do you think brought about these problems? (probes: is it the HIVST kit, you are asking him to test? test results)
5. What kind of support do you think you and your partner need to help with these problems? (Where can you get it from and who can provide you with that kind of support? Probe on providers- CWH, Health care workers and the type of counselling needed(Telephone counselling, Individual counselling, Couple counselling, Family counselling)
6. How best can we prevent these problems in other families?

##### **For clients that did not experience social harms:**

7. After you offered the test kit to your partner, you mentioned to us that this did not bring any problems in your home. How is the situation now from the last time we talked, did you face any problems with your partner because of you offering the test?
8. Has your relationship changed in any way after our last discussion?
9. **If the client did not experience any social harms:** Why do you think you did not experience any problems with you giving the test kit to your partner?
10. **How best can we help families that have such problems?**

#### **B. Linkage to care Experiences of being on ART [ for clients testing positive]**

1. From the last time we talked, has your partner now linked to care? (probes:
2. What has been experiences with being on ART now? (probes: any challenges with adherence

3. How has your relationship changed now that he is on ART?
4. How does it feel for you who brought him the test kits and with it he tested and then got the results that he has now? [probes: do you feel guilty, happy that he is on ART now)  
**If partner tested negative, ask:**
5. Did your partner access prevention services- condoms, VMMC, PMTCT (for those who tested negative and are willing to share experience) Probe: where? From who?
6. Do you have anything to add or suggest?
7. We have come to the end of the interview.

We have come to the end of the interview. Thank you

## **Qualitative-Cohort: In-depth Interview for Index partner (second interview)**

**Recap of the last interview:** Last time we talked about to you about your experiences of receiving the test kit from your partner. Our discussion today is just a follow up to see how you are doing and what has changed after our first interview:

### **A. Social harms**

#### **For clients that experienced social harms**

1. After you were offered a test kit by your partner, you mentioned to us that this brought about some problem in your home. Apart from what you told us last time, did you experience any additional problems with your partner? (Probe: on the last harms that were reported)
2. Has your relationship with your partner now changed in any way after our last discussion?
3. What is it that made you and your partner experience these problems? (her/him giving the test kit to you, not getting permission from you before getting the kit, the way she delivered the test kit to you, suspecting you of cheating, was it the test results)
4. Looking back on what happened, how did you sort out these problems? (Probes: who did you consult? clinic staff, CHW, family members etc.)
5. Looking back on what happened, is there anything you can do differently now?
6. What kind of support do you think you and your partner need now to help with these problems? (Where can you get it from and who can provide you with that kind of support? Probe on providers- CWH, Health care workers and the type of counselling needed(Telephone counselling, Individual counselling, Couple counselling, Family counselling)
7. How best can we prevent these problems in other families?

#### **For clients that did not experience social harms:**

8. After you were offered a test kit by your partner, you mentioned to us that this did not bring any problems in your home. How is the situation now from the last time we talked, did you face any problems with your partner because of you offering the test?
9. Has your relationship changed in any way after our last discussion?
10. Why do you think you did not experience any problems with your partner after you were given a test kit?
11. How best can we help families that have such problems?

### **B. Linkage to care Experiences of being on ART [ for clients testing positive]**

1. From the last time we talked, have you now linked into care? (Probes: how long did it take for you to decide to start ART? how long did it take the clinic to start you on treatment?)

2. What has been your experience with being on ART now? (probes: any challenges with adherence, challenges with access ART from the clinic)
3. Has your relationship changed now that he is on ART?

If tested negative, ask:

4. Did you access prevention services- condoms, VMMC, PMTCT (for those who tested negative and are willing to share experience) Probe: where? From who?
5. Do you have anything to add or suggest? Thank you

We have come to the end of the interview. Thank you

## **FGD for Secondary distribution models (ART and ANC)**

### **FGD with Community Members for secondary Distribution Models**

Thank you for taking time to speak with me today. My name is \_\_\_\_\_ and I am working with Zambart. To increase the uptake of HIV services, HIV self – testing kits are being distributed at the ARTs clinic and ANC. We would like to hear what you think about this as well as what the community thinks. We will record the interview to make sure that we capture all the valuable information that you share with me. We will also be taking down notes so that I do not forget what we have discussed. Please feel free to give honest answers as what we say is confidential. We will not record your name on the tape or on the notes that will be written and no one else will see the tape or the notes besides people who are working on this research project.

#### **A. Physical Factors**

1. What do you think of the place (ANC and ART hub) where people collect the HIVST kit? (Probe: conducive, comfortable)
2. What do you think of the space where HIVST kit collection is being done? (Probe; appropriateness)
3. What do you think about the time of the distribution of kits? (Probe: is it ok, could it be changed, could you suggest the best time)

#### **B. Community/Social factors and stigma**

1. What other testing services are available in this community?
2. How did the availability of other testing services other than HIVST affect people's decision?
3. How does the anticipation of what people may say after someone tests using HIVST influence the decision? What do you expect people to say?

#### **C. Process of delivering the kit to partner**

1. How do you feel about this program of distributing kits through ANC/ART clinic?
2. What do people say about collecting kits for their partner from (ANC/ART CLINIC?)
3. How did women/men feel about being the ones to give their partner a kit? (Comfortable why, not comfortable why)
4. How did men/women feel about receiving a kit from their partner?
5. Why do you think people decided to collect the kit for their partners?
6. What are the advantages of collecting the kit for your partner?
7. What are the disadvantages of collecting the kit for your partner?
8. Describe how the process of giving kits to partners has been in the community

**D. Power and social relations**

1. Did the relationship among partners influence the decision to test?
2. How has bringing of the test kit by some partner affect relationships in the community (support, trust, anger, violence)
3. How do societal beliefs influence decisions? What beliefs/ issues influenced your decision? (Masculinity, religion,)

**E. Equity**

1. Who is accessing these services (Collecting of kits and using them?)
2. Why are they accessing the service?
3. Is there a group of people who want to access the service but are failing? (Why?)
4. What can the community do to help such people access the service?
5. What can the health workers do to help such people access the service?
6. Are certain groups of people accessing the kits more than the other?

**F. Linkage to care**

1. Do you think are people going for a confirmatory test? Can anyone share an experience (what influenced the decision, where was the test conducted if you have done it). Probe: trust of test kit, partner support,
2. How easy or difficult do you it is to have a confirmatory test done? Probe: availability of testing services, location of testing services, stigma, attitude of HCWs,
3. (For those who are negative) How easy or difficult was it to access prevention services- condoms, VMMC, PMTCT (for those who tested negative and are willing to share experience)
4. Do you know anyone who has started treatment because of secondary distribution?
5. (**For those who have started treatment**) What factors may have facilitated their decision to start treatment? Probe:
6. (**For those who have not started treatment**) What factors may have hindered their decision to start treatment? Probe:
7. In your opinion, what are the other barrier of linkage to confirmatory testing and care?
8. What can be done to help people who receive kits through their partner link to care?

**G. Social harms**

1. Where there any unfavourable outcomes of giving the self - test kit to a partner by a partner? (Probe experiences gender-based violence, humiliation, stigma or discrimination)
2. What role did partners play as their partners tested using the test kit? How influential were partner in the process? (Probe if the participant experienced forced testing, forced disclosure, was supervised during testing when they did not want to)
3. How can such incidents be prevented?
4. How can they be detected?

5. Where can one report such incidents?
6. What can the community do to prevent such harms?

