## **4.2 Qualitative methods**

Qualitative data collection will begin with implementation of participatory activities through community consultation processes and stakeholder discussion, followed by IDI, FGD, mapping, and observation of HIVST distribution (Table 2). Qualitative data will provide understanding of contextual factors that mediated people's choices and behaviour. The qualitative research will explore the following themes:

1. Social support and social networks (friends, workmates, church, customs, support after testing, attitudes of HCWs)
2. Livelihood options
3. Knowledge of HIV testing and HIVST, and individual attitudes towards HIV testing and HIVST
4. Power relations, social harms and gender-based violence within couple/partners
5. Social effects of HIVST including stigma
6. Location and lay-out of distribution points, including community social and physical features
7. Environmental factors (flooding, disease outbreaks, strikes etc.)
8. Promotion and social marketing

A total of 12 FGDs and 46 IDIs will be conducted (see table 2 for distribution). Both the FGDs and IDIs will be conducted by trained RAs with the help of a Junior and senior social scientist. The Neighbourhood Committee (NHC) members will help to identify appropriate venues within the community. The NHC is a community-based organisation created by an act of parliament to ensure community involvement in the management of health related programmes in the community. The size of the focus groups will be between 8-12 participants. This is the recommended size to ensure interaction between the participants. Focus group discussion and IDI participants will be selected purposively for each distribution model, aiming for a range of ages, men and women, and individuals who accepted or declined an offer of HIVST. The composition of the FGDs is described in section 5.1 (recruitment of qualitative study participants). In addition 4 stakeholder discussions with representatives of community based groups and 15 observations of the mechanisms of distribution and interactions between distributors and clients will be conducted.

Twelve individuals from each of the quantitative cohorts linked to secondary distribution methods (24 in total) will be purposely selected to take part in the Secondary Distribution qualitative cohort. They will be interviewed at two points: at recruitment and follow-up.

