### 5.1 Recruitment of qualitative study participants

In total 46 IDIs, 12 FGDs, 4 stakeholder meetings and 15 observations will be conducted. The 42 IDIs will be conducted with purposefully selected individuals accessing VMMC (6), facility/ community-led (6), work places (6) ANC (12) HIV+ individuals (12) and health care workers (4). The 12 FGDs will be conducted with purposely selected community members to obtain community perspectives on the different models; 4 for the ANC model, 4 for HIV+ individuals' model, 1 for VMMC model, 2 for facility-led/community-led model and 1 for the workplace model. Of the 4 FGDs for the ANC model, 2 will be composed of individuals attending the ANC at the clinic and the other 2 of ordinary community members (women) recruited from the community. Similarly, the 4 FGDs for HIV+ will be divided into 2 (mixed sex) for individuals attending ART recruited from the clinic and the other 2 ordinary community members (mixed sex) recruited from the community. The VMMC and work place FGDs will be composed of individuals about to undergo VMMC and staff of work place. Stakeholder meetings will be conducted with representatives of different groups identified during community consultations. The four HCWs who are involved in distributing HIVST will be purposely selected (to ensure a

mix of gender and type or aspect of the model they are involved in) to take part in qualitative interviews. They will be asked for their perspectives on HIVST and the distribution models, linkage to care and prevention services, social harms and sustainability of the models. The study will be explained to them and consent obtained before taking part in the study. Other HCWs may take part in stakeholder meetings at the beginning of the study if the clinic/ HCWs are identified as key stakeholders in HIV care and prevention activities in the community.

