### **8.4 Privacy and Harm Reduction**

All efforts will be made to ensure that participants are provided with privacy when answering questions which may be sensitive. The research assistants will be trained to work with the participant to ensure a safe and private space is available, either in the participants' home, the facility or if this is not possible in another place of the participants' choice.

Some questions, such as those about violence and social harms are especially sensitive and will require special training of the research assistants. Research assistants will be equipped with information about access to services available in the communities for individuals experiencing violence and social harms, and will be trained to refer and support any participants who have experienced violence. The questions about violence and also about relationships and power within relationships are critical to the understanding of the safety and applicability of secondary distribution of HIV test kits and so are asked for this purpose only. All participants will be reminded that they can decline answering any questions at any time.

A social harm reporting system will be maintained in research areas and will be based on earlier social harms reporting systems developed by Zambart and SFH for the PopART trial and STAR. Potential social harms will be evaluated for seriousness, and likely relatedness to HIVST by the study PI. Social harms reporting, and investigation will take into account confidentiality and anonymity. Tracking of social harms will then enable SFH/Zambart to assess and mitigate adverse events arising from HIVST.

All social harms are reported to the STAR Initiative's independent Technical Advisory Group. Social harms related to HIVST will also be reported to the ethics committees.

The Standard Level of Serious Adverse Event will be used [25] for reporting the following serious adverse events to study leadership within two working days of becoming aware of the event:

- 1 Death;
- 2 Disabilities/incapacities;
- 3 Hospitalisations that are “suspected adverse drug [procedure] reactions” (cannot rule out relationship to study procedures), or
- 4 Other Grade 4 events that are “suspected adverse drug [procedure] reactions” (cannot rule out relationship to study procedures).

Annual reports with full listings of SAEs will also be submitted to Ethics Review Boards.

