**E. Linkage to care**

1. Do you think are people going for a confirmatory test? Can anyone share an experience (what influenced the decision, where was the test conducted if you have done it). Probe: trust of test kit, partner support,
2. How easy or difficult do you it is to have a confirmatory test done? Probe: availability of testing services, location of testing services, stigma, attitude of HCWs,
3. (For those who are negative) How easy or difficult was it to access prevention services- condoms, VMMC, PMTCT (for those who tested negative and are willing to share experience)
4. Do you know anyone who has started treatment as a result of secondary distribution?
  - a. (For those who have started treatment) What factors may have facilitated their decision to start treatment? Probe:
  - b. (For those who have not started treatment) What factors may have hindered their decision to start treatment? Probe:
5. In your opinion, what are the other barrier of linkage to confirmatory testing and care?
6. What can be done to help people who receive kits through their partner link to care?

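### Some focus-group questions invite participants to disclose their own HIV result or coercion in front of the group, against the privacy promised in section 8.4

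*Protocol*

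**What the plan says.** Protocol section 8.4 states: "All efforts will be made to ensure that participants are provided with privacy when answering questions which may be sensitive". It goes on to single out violence and social harms as especially sensitive, and lets anyone decline a question. Section 4.2 says that the focus groups are held to obtain community perspectives, and that "The size of the focus groups will be between 8-12 participants".

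Appendix 4 prints two focus-group guides, one for the secondary-distribution models and one for the community-led models.

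- **Coercion.** Under social harms, item 2 of the secondary-distribution guide has the facilitator "Probe if the participant experienced forced testing, forced disclosure, was supervised during testing when they did not want to". The community-led guide has no such probe.
- **Confirmatory testing.** Under linkage to care, item 1 of both guides asks: "Can anyone share an experience (what influenced the decision, where was the test conducted if you have done it".
- **Result-keyed question.** Under linkage to care, item 3 of both guides reads: "For those who are negative) How easy or difficult was it to access prevention services- condoms, VMMC, PMTCT". The sentence then limits itself to people who tested negative and are willing to share.
- **Violence.** Under social harms, item 1 of both guides asks about unfavourable outcomes in general terms, then probes experiences of gender-based violence, humiliation, stigma or discrimination. It does not say whose experiences are meant.

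Section 5.1 gives the number of groups ("4 for the ANC model, 4 for HIV"-positive individuals, plus 2 for the facility- and community-led model) and describes some of them as "2 (mixed sex) for individuals attending ART recruited from the clinic".

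**The concern.** A focus group drawn from one clinic or community cannot offer the privacy that section 8.4 promises. If the facilitator asks a person there about having been forced to test or to disclose, or asks for an account of that person's own confirmatory test, the answer is heard by people who may know the speaker. The protocol itself treats coercion to disclose a self-test result as a social harm (Grade 2 in the grading table of Appendix 4), and section 10.2 recognises gender-based violence and coercion as risks of secondary distribution. A guide that draws out such disclosures in company could cause harm of the kind the study sets out to monitor.

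**Working it through.** No figure in the plan is in dispute. The check compares the texts and counts the people reached.

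**1. Group guide against one-to-one guide.** The coercion probe in the secondary-distribution focus-group guide (social harms, item 2) is word for word the probe in the one-to-one guide for the primary partner (power, social relations and social harms, item 3). In the group guide the lead question was recast to ask about partners in general, but the bracketed probe still refers to the participant. The one-to-one guide also tells the interviewer, at the head of its linkage section, to establish first whether the person is willing to talk about HIV status. Neither focus-group guide has that opening step.

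**2. What answering can reveal.** Section 3 says that a reactive self-test needs confirmatory testing and a non-reactive one does not. Someone who describes their own confirmatory test therefore implies a reactive self-test. The closing words of item 1's bracket turn the question on the speaker. Item 3 opens by addressing people with a negative result, so replying states a result.

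**3. Opening scripts.** Both focus-group scripts tell participants that what is said is confidential. Neither asks the group to keep what it hears private, and neither says that a question may be skipped. The mapping guide for the Neighbourhood Health Committee, in the same appendix, does tell people they may leave a question unanswered.

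**4. People reached.** Inputs are the group size of 8 to 12 (section 4.2) and the numbers of groups (section 5.1). Each speaker sits with 7 to 11 others.

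- Coercion probe: 4 + 4 = 8 groups; 8 × 8 = 64 to 8 × 12 = 96 people.
- Violence probe and the two linkage items: the same 8 groups, plus the 2 facility- and community-led groups; 2 × 8 = 16 to 2 × 12 = 24 more people.
- Added risk of revealing HIV status: in the 2 groups of ART clients, positive status is already implied by membership. That leaves 10 − 2 = 8 groups where the risk mainly lies: 2 of ANC clients, 2 of community women, 2 of community members for the HIV-positive model, and 2 facility- and community-led. These hold 8 × 8 = 64 to 8 × 12 = 96 people, a different set from the 64 to 96 above.

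**The case against.** The strongest reply is that this is one leftover probe in guides that are otherwise mostly impersonal. The treatment questions ask whether participants know anyone who started treatment. The lead questions on harm speak of partners in general. Item 3 is limited to those willing to share, item 1 is an open invitation, and section 8.4 adds special training of the research assistants, referral and the right to decline. Written consent is taken for focus groups, and the consent forms are not among the pages available, so a warning about group confidentiality may exist there.

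Much of this stands. It lowers the risk and keeps the point small. It does not remove it, because a probe aimed at the participant's own coercion and a question about one's own confirmatory test still conflict with section 8.4 when asked in a group.

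A reader might infer more than the documents support:

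- **That silence on item 3 marks someone as positive.** Section 5.1 allows community members who have not yet accessed HIVST into focus groups. Silence may mean never tested, no service sought, or unwilling to speak.
- **That harm reports will be biased downward.** The documents do not use focus groups to estimate a rate of harm. Harms are also asked individually in the one-month follow-up questionnaire and the one-to-one interviews. At most, reticence may thin the focus-group narrative.
- **That the 3% coercion figure in section 10.2 gives an expected number of affected participants.** It comes from volunteer-counsellor distribution in Malawi, cited as evidence on primary distribution, and does not fit index clients and community members.

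**Conclusion.** The point holds as a conflict of wording within the protocol. The clearest defect is the personal coercion probe, which stands in one group guide only. Linkage items 1 and 3 in both guides come next. The violence probes are the mildest case, since their lead question is already impersonal and only the reference of the probe is unclear.

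The exposure is 64 to 96 people for the coercion probe, and a further 16 to 24 for the other items. This assumes that the secondary-distribution guide is used in all eight of its groups and the community-led guide in the two facility- and community-led groups. The protocol does not say which guide serves the VMMC and workplace groups, so they are not counted. These are numbers of people who would meet the questions, not numbers expected to disclose or be harmed; the documents give no basis for the latter.

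**What to change.** In Appendix 4:

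- Secondary-distribution focus-group guide, social harms item 2: delete the probe on the participant's own coercion, or recast it to ask whether such things happen to people in the community.
- Both focus-group guides, linkage items 1 and 3: ask what happens to people in this community after a self-test. Remove the closing words of item 1's bracket that turn to the speaker, and the opening label of item 3 that addresses people with a negative result.
- Both focus-group guides, social harms item 1: state that the violence probe concerns the community.
- Both opening scripts: add a line asking participants not to state their own HIV result or experience of violence in the group.
- Keep the first-person questions in the one-to-one guides, where they already stand (the index partner's section on social harms; the primary partner's sections on linkage and on power, social relations and social harms).

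This costs a few reworded items and one script line per guide. The downside is fewer first-person accounts from the groups, which the one-to-one interviews already collect in private.
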